10.5. FIT treatment sessions

A detailed description of the full protocol for the FIT treatment sessions is provided in a separate manual. After each session, the ALN will record on an eCRF whether the session was completed, the date, time and duration of the session and whether the session was audio recorded for fidelity assessments (see section 10.5.5). In brief the following sessions take place.

10.5.1. Session 1 (in-patient)

This in-patient face-to-face session takes place at any time from randomisation to date of hospital discharge.

This session lasts less than 60 minutes and introduces mental imagery as a skill people can use to help them achieve their goals. The ALN uses active listening skills to elicit the participant's personal incentives for change, to explore the discrepancy between how they are now and how they want to be in the future, and to elicit ideas about how to change. Mental imagery is used at each point to strengthen desire for change; to mentally rehearse plans and strengthen commitment to them; to explore ways to overcome barriers; to strengthen confidence by replaying past successes and strategies.

10.5.2. Session 2 (face-to-face)

This second face-to-face session takes place within 10 days of discharge from hospital

The session lasts less than 45 minutes and is included to support motivation early after hospital discharge. This session will take place in the hospital outpatient department to review progress. Imagery is used to help solve any problems with progress towards their goal and to motivate new subgoals. Individuals who experience strong cravings are taught how to switch their attention deliberately away from their craving imagery and onto their goal imagery.

There is an option to conduct this session by telephone or virtually, in the situation where local or national lockdown measures are implemented to control COVID-19 or after an appropriate risk assessment in made by the local R&D department necessitating reduced footfall within hospitals.

10.5.3. Session 3 (by telephone)

This session takes place at Day 14 (±4 days) post-hospital discharge

The ALN will contact the participant by telephone as described in section 10.6. This session lasts less than 30 minutes. Booster calls affirm progress, develop imagery about recent successes, problem solutions, new goals or behaviours, and encourage practice.

10.5.4. Sessions 4-9 (by telephone)

These six sessions take place at Days 28, 42, 56, 90, 120 and 180 (all \pm 7 days) post-hospital discharge.

The ALN will contact the participant by telephone as described in section 10.6. All sessions last less than 15 minutes.

10.5.5. Intervention fidelity assessment

Where participants consent, FIT and TAU sessions will be audio recorded for fidelity checking and assessment of contamination. Sampling for fidelity assessment will take place as follows:

- Two FIT sessions will be assessed per ALN (one each from Sessions 1 and 2) from the first five participants and two FIT sessions per ALN (one each from Sessions 1 and 2) from the next five participants.
- Two TAU sessions will be assessed per ALN from each of the first and second sets of five participants.

A trained FIT practitioner will check each ALN's fidelity early in the trial using dedicated fidelity assessment tools previously developed. Feedback and supervision will be provided through these sessions. These fidelity assessments will also examine the potential for contamination due to the same ALNs providing both TAU and FIT.

10.6. Contacting participants for research and treatment visits

A member of the site team (ALN or research team member) will contact the participant by phone at an agreed time. If the participant does not answer, and they have a voicemail service, a short message will be left asking the participant to call back. If they do not call back, or there is not a voicemail service, a second attempt will be made on the same day to the primary contact number of the participant. Failure to be contacted on the second attempt will result in a third attempt on the primary contact number within the following 3 days. If it is still not possible to contact the participant on the third attempt, the secondary contact number will be called and a different contact time organised with the participant via the secondary contact if possible. Where the participant can still not be contacted, no further attempts will be made until their next scheduled visit.

The participant's GP may be contacted by a member of the site team at this point to check patient status.

11. QUALITATIVE ASSESSMENTS

11.1. Participant interviews

Short telephone interviews will be conducted in the first three months of recruitment, with those who were eligible but declined to take part (n=6, 2 from each recruiting site) to identify their reasons for this. At the time they declined to participate in the trial, eligible patients will be asked if their contact details can be retained so that they can be contacted by a named researcher to take part in a voluntary telephone interview.

At the end of the trial, after follow-up visits have been completed, participants who agreed to be further contacted to take part in an interview (control, n=6; intervention, n=9) will be interviewed by telephone to inform our understanding of acceptability and feasibility of trial methods. There will be a focus on study materials, motivation for taking part, understanding and experience of randomisation and, additionally, for intervention participants, engagement with FIT.

At least 24 hours before the interview takes place, the selected interviewees (i.e. patients who declined to take part and participants who completed the study) will be given a separate information sheet describing what is involved in the interview and what will happen to their data. Informed consent will be obtained either in writing by returning the signed informed consent form by post to the researcher at the University of Plymouth or by audio recording of verbal consent. Participants who consent to a telephone interview at the end of the trial will be sampled equally from each site and those in the intervention arm will be balanced according to engagement in FIT treatment (those who completed the >4 FIT sessions versus those that did not).

11.2. Research nurses

Research nurses involved in collecting trial data will be invited to virtual meetings monthly during the first three months of recruitment (which will include the first two months of follow up assessments) to assess recruitment and retention rates and use interview data from patients who declined to take part to inform strategies to enhance both. Detailed notes will be made of the meetings, including any proposed changes to recruitment and retention strategies and impact.

11.3. ALNs

All ALNs participating in the study will be invited to take part in two 60-minute virtual focus groups, one early and one later in the intervention delivery phase of the trial. They will be provided with a written information sheet detailing the purpose of the focus groups and what will happen to their data at least 24 hours before the first focus group. Informed consent will be obtained either in writing by returning the signed informed consent form by post to the researcher at the University of Plymouth or by audio recording of verbal consent. The objectives of these discussions are:

- To assess the acceptability and utility of FIT training, manual and supervision
- To identify barriers and facilitators to FIT delivery
- To identify methods to improve delivery and implementation within the NHS

11.4. Qualitative analysis

Telephone interviews will be recorded and transcribed verbatim and uploaded to NVivo 12 software for organisation and analysis. Data will be analysed using thematic analysis adopting Braun and Clarke's six-phase process of (i) data familiarisation; (ii) coding; (iii) generation of initial themes; (iv) reviewing themes; (v) defining and naming themes and (vi) writing up to identify patterns of meaning within the data sources.

12. ECONOMIC EVALUATION

This pilot study will be used to test the methods for a subsequent, policy-relevant, cost-effectiveness analysis (CEA) of FIT and TAU, compared to TAU. This future economic evaluation will be undertaken

IRAS ID: 293042

alongside the full RCT and will establish the resources required to provide the FIT intervention, estimate intervention costs, and conduct a full CEA. The intervention costing and CEA, based on within-trial data collection, will be undertaken against a primary perspective of the NHS/Social Care, with participant and broader societal perspectives considered in sensitivity analyses. The future CEA will synthesise cost and outcome data to present an incremental cost-effectiveness ratio (ICER) for the primary economic endpoint of policy relevance (cost per quality-adjusted life-year [QALY]). The economic evaluation will follow the internationally recognised Consolidated Health Economic Evaluation Reporting Standards (CHEERs) guidelines for reporting cost-effectiveness studies.⁵¹ A Health Economics Analysis Plan (HEAP) will be developed and agreed prior to database lock.

12.1. Intervention costing

The resources required to deliver the FIT intervention will be assessed via participant-level caserecords, and discussion with the intervention developers and providers. This will include ALNs' time, travel, materials, documentation and consumables. ALNs' time will be documented in terms of perparticipant contact and non-contact time, and any additional time in relation to delivery of the intervention. Training and supervision resources will also be documented.

Nationally recognised UK unit costs for health and social care services⁵² will be applied to this resource use data. Where national costs are not available, costs will be identified in consultation with the intervention developers and providers. The mean cost per participant of the intervention will be estimated.

12.2. Health, social and wider care resource use

A self-report bespoke resource use questionnaire will be developed with our PPI group. This questionnaire will also be informed by the Database of Instruments for Resource Use Measurement (DIRUM)⁵³ and the core items for a standardised resource use measure.⁵⁴The questionnaire will be completed by participants at baseline and Day 90 and Day 180 follow-ups.

12.3. Quality-adjusted life-years

Participants will complete the EQ-5D-5L⁵⁵ at baseline and at Day 90 and Day 180 follow-ups. The EQ-5D is a generic measure of health-related quality of life. It is the instrument recommended for use by the National Institute of Health and Care Excellence (NICE) in health technology assessments to estimate the cost-per-QALY of interventions and to inform healthcare policy across the NHS. In accordance with the current 'position statement' of NICE,⁵⁶ the 'approved' cross-walk algorithm will be used to map EQ-5D-5L responses to the EQ-5D-3L health state utility value set to estimate participant-level QALY weights.^{57,58}

13. PARTICIPANT WITHDRAWAL

13.1. Withdrawal from treatment

Given the low risk of harm posed by FIT therapy, withdrawal of the FIT intervention on the grounds of safety or wellbeing concerns is not foreseen. However, if the PI (or authorised delegate) identifies deterioration in psychological state or other relevant medical concerns, s/he may choose to discontinue the FIT treatment.

Participants may choose to withdraw themselves from FIT or TAU intervention at any stage of the trial. In this case, participants will be asked to provide a reason for withdrawal but must be made aware that they are not obliged to give a reason and that their decision to withdraw will not affect their ongoing treatment.

Withdrawal from FIT or TAU and the reason, if known, should be clearly documented in the participant's clinical records and reported to the CTU according to instructions provided.

Withdrawal from treatment does not preclude the participant from remaining in follow-up. All participants withdrawn from FIT or TAU will be encouraged to continue with study visits and assessments as per protocol.

13.2. Withdrawal from follow up

All participants will be encouraged to complete study follow-up, but participants may choose to withdraw from follow-up at any time. In this case, participants will be asked to provide a reason for withdrawal but must be made aware that they are not obliged to give a reason and that their decision to withdraw will not affect their ongoing treatment.

Withdrawal from trial follow-up and the reason, if known, should be clearly documented in the participant's clinical records and reported to the CTU according to instructions provided. Data collected prior to withdrawal from follow-up will be included in the study analysis. Participants will be provided with a contact point where he/she may obtain further information about the study.

Withdrawn participants will not be replaced with new participants.

14. END OF TRIAL DEFINITION

Participants will complete their involvement in the trial after approximately six months, at either the end of trial visit, approximately 180 days after the baseline visit, or at the end of the final FIT delivery session (if in the intervention group), approximately 180 days after hospital discharge. A sample of participants will be selected to take part in qualitative interviews (see section 11). The trial will end on completion of all data collection, including qualitative interview data.

15. COLLECTION, STORAGE AND ANALYSIS OF CLINICAL SAMPLES

It is the responsibility of the trial site to ensure that samples are appropriately labelled in accordance with the trial procedures to comply with the 2018 Data Protection Act. Biological samples collected from participants as part of this trial will be transported, stored, accessed and processed in accordance with national legislation relating to the use and storage of human tissue for research purposes and such activities shall at least meet the requirements as set out in the 2004 Human Tissue Act and the 2006 Human Tissue (Scotland) Act.

The following clinical samples will be obtained:

• A urine sample for direct alcohol metabolites - at Day 180

Detailed instructions on the collection, recording and processing of samples will be provided to sites in a separate manual, provided by PenCTU.

15.1. Urine

A sample of 10 mL mid-stream urine will be collected into a sterile universal container. It will be stored locally at each site at between -20°C and -80°C in a temperature monitored freezer. After the final trial visit is completed at each site, urine will be sent in a single batch to the Viapath laboratory at King's College Hospital, London for analysis of ethyl glucuronide and ethyl sulphate by liquid chromatography tandem mass spectrometry.

15.2. Destruction of samples

Any samples remaining after the planned analyses will be destroyed in accordance with laboratory standard operating procedures.

16. SAFETY MONITORING

Whilst participants are unlikely to experience any harm as a direct result of taking part in this trial, processes will be implemented to ensure that such harms are detected and monitored appropriately. The safety of participants will be monitored throughout the trial, from the time that consent is obtained until the end of trial visit.

16.1. Definitions

An **Adverse Event (AE)** is any unfavourable sign, symptom, or disease in a participant, regardless of severity and regardless of cause.

An **Adverse Reaction (AR)** is an adverse event which is considered to have been definitely, probably or possibly caused by either the FIT intervention or the trial procedures.

A Serious Adverse Event (SAE) or Serious Adverse Reaction (SAR):

- results in death
- is life-threatening*
- requires inpatient hospitalisation or prolongation of existing hospitalisation**
- results in persistent or significant disability/incapacity
- is a significant or important medical event

*The term "life-threatening" in this context refers to an event in which the participant was at risk of death at the time of the event; it does not refer to an event which hypothetically might have caused death if it were more severe.

Hospital admissions for elective procedures **will not be reported as SAEs. All unplanned hospital admissions will be reported as SAEs, regardless of duration of hospital stay. This includes visits to ED departments.

A Suspected Unexpected Serious Adverse Reaction (SUSAR) is an event which:

- is serious, as defined above, and
- is considered to have been definitely, probably or possibly caused by either the FIT intervention or the trial procedures, **and**
- is deemed 'unexpected' i.e. the reaction is one which has not been foreseen by the Chief Investigator.

Guidance on assessing events against these definitions is described later in this section.

16.2. Adverse event reporting in the MIRAGE trial

The likelihood of participants being harmed by either the FIT intervention or any of the trial procedures is very low. As such, the collection and reporting of adverse events in the MIRAGE trial is restricted to only those events which are serious, as defined above. In the context of clinical care and in accordance with local practice, adverse events should be recorded by investigator site staff in the participants' medical records. For the purposes of the trial, only serious adverse events (including serious adverse reactions) will be collected and entered into the eCRF.

16.3. Detecting and recording serious adverse events

Detailed instructions for the recording and reporting of serious adverse events will be provided to Investigator Sites by PenCTU.

The primary means of detecting serious adverse events will be the interactions between the research team member(s) and the trial participant at each of the data collection timepoints. At each visit or telephone call, participants will be asked to describe any adverse events they have experienced.

Any events meeting the criteria for seriousness (defined in section 16.1) must be recorded by the research team member in the participant's health record and in the eCRF. SAEs are subject to expedited reporting so must be processed in a timely manner (see section16.5).

The Day 90 and Day 180 timepoints involve collection of health and social care resource utilisation. Site researchers should ensure any (non-elective) hospitalisations or ED visits reported by participants when recalling resource utilisation are reported as serious adverse events.

16.3.1. Serious adverse events detected by ALNs during FIT sessions

ALNs may also become aware of hospitalisations experienced by participants if discussed during FIT intervention sessions. In the event that an ALN believes a participant has suffered a serious adverse event caused by the FIT intervention or by any trial procedures, s/he must report immediately to the site Principal Investigator, who will enter the event into the eCRF according to instructions provided by CTU.

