16.4. Assessing causality of serious adverse events

For serious adverse events, the PI (or authorised delegate) will assess the causal relationship between the SAE and trial participation.

For participants in the intervention group, the PI will record their opinion on whether or not the SAE was caused by the FIT intervention, and whether or not the SAE was caused by any trial procedures. For participants in the control group, the PI will record their opinion on whether or not the SAE was caused by any trial procedures.

Causal relationship will be recorded in the participant's health record and in the eCRF. SAEs caused by the intervention or trial procedures in the opinion of the PI will be regarded as serious adverse reactions (SARs).

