16.5. Reporting Serious Adverse Events and Serious Adverse Reactions

All SAEs and SARs must be reported to PenCTU within 24 hours of the research staff becoming aware of the event, according to instructions provided by PenCTU.

For each SAE/SAR the following information will be collected:

- full details in medical terms and case description
- event duration (start and end dates, if applicable)
- action taken
- outcome
- seriousness criteria
- causal relationship

PenCTU will immediately notify the CI of any reported SAEs / SARs and the CI will record a second assessment of causal relationship. The CI may upgrade the causality assessment (e.g. from not related to related) but may not downgrade the assessment (e.g. related to not related).

Where a causal relationship is suggested, the CI will record an assessment of expectedness. Expectedness will be judged on a case-by-case basis.

An event deemed to be unexpected will be regarded as a SUSAR and will be subject to expedited onward reporting as described in sections 16.6 and 16.7.

Events will be followed up until the event has resolved or a final outcome has been reached.

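### Section 16.3.1 makes the alcohol liaison nurse's only written duty to report a serious event depend on that nurse's own view of its cause, in conflict with 16.1, 16.4 and 16.5, so events first disclosed in a FIT session may reach the PI late or be missed.

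*Protocol*

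**What the plan says.** The rules are spread over five subsections of Protocol section 16.

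- **16.1 Definitions.** "All unplanned hospital admissions will be reported as SAEs, regardless of duration of hospital stay". Emergency department visits are included and only elective procedures are left out. Cause plays no part in whether an event is an SAE.
- **16.3 Detection.** "The primary means of detecting serious adverse events will be the interactions between the research team member(s) and the trial participant" at each data collection timepoint. Anything serious found there "must be recorded by the research team member in the participant's health record and in the eCRF". Non-elective admissions and emergency visits recalled in the day-90 and day-180 resource-use questionnaire must also be reported as SAEs.
- **16.3.1 ALNs.** "ALNs may also become aware of hospitalisations experienced by participants if discussed during FIT intervention sessions". The duty to report immediately to the site PI applies where "an ALN believes a participant has suffered a serious adverse event caused by the FIT intervention or by any trial procedures". Nothing is said about other serious events.
- **16.4 Causality.** "the PI (or authorised delegate) will assess the causal relationship between the SAE and trial participation".
- **16.5 Reporting.** "All SAEs and SARs must be reported to PenCTU within 24 hours of the research staff becoming aware of the event". Then "PenCTU will immediately notify the CI of any reported SAEs / SARs and the CI will record a second assessment of causal relationship". The CI may raise the causality rating but not lower it.

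Section 10.6 treats the ALN and the research team member as separate members of the site team. Section 10.5.4 places FIT sessions 4 to 9 at days 28, 42, 56, 90, 120 and 180 after discharge. SAP 5.4 reports SAEs by treatment group.

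**The concern.** An unplanned admission mentioned in a FIT session is an SAE under 16.1 the moment it is known. Under 16.3.1 the ALN need pass it on only after concluding that FIT or the trial caused it. That conclusion belongs to the PI and then the CI, and the ALN who reaches it first is the person who delivered the therapy, working under a protocol that says no adverse effects of FIT have been reported (section 3).

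The CI's upgrade-only review exists to catch related events that were under-called, but it cannot act on an event that was never passed on. At stake are the timeliness and completeness of SAE capture for events first disclosed to the ALN, in a trial with no data monitoring committee.

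**Working it through.** The plan gives no figure on this point to reproduce. The check sets the passages side by side, then sizes the possible delay.

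**Step 1: the same event under each rule.** Take an unplanned admission that a participant first mentions in a FIT session and that the ALN thinks is unrelated.

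| Rule | Result |
|---|---|
| 16.1 | It is an SAE; cause is irrelevant |
| 16.3 | If told to a research team member, it must go in the eCRF |
| 16.3.1 | If told to the ALN, no written duty to pass it on |
| 16.4 and 16.5 | PI, then CI, judge cause, but only once the event reaches them |
| 16.5 clock | Starts with awareness by research staff; given 10.6, it is unclear whether an ALN's knowledge counts |

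The ALN's threshold also differs from the protocol's own. Section 16.1 counts an event as a reaction if a causal link is even possible; 16.3.1 speaks of an event believed to have been caused by FIT or the trial. A possibly related event can meet the first test without triggering the second.

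**Step 2: wait until the next scheduled research visit.** Inputs: FIT session days after discharge (10.5.4) and research visits at days 28, 90 and 180 after baseline (10.2 to 10.4). The interval from baseline to discharge, *d*, is not given; I assume 2 to 14 days.

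Formula: wait = research visit day − (session day + *d*).

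| Session day after discharge | Next visit | *d* = 2 | *d* = 14 |
|---|---|---|---|
| 28 | 90 | 90 − 30 = 60 | 90 − 42 = 48 |
| 42 | 90 | 90 − 44 = 46 | 90 − 56 = 34 |
| 56 | 90 | 90 − 58 = 32 | 90 − 70 = 20 |
| 90 | 180 | 180 − 92 = 88 | 180 − 104 = 76 |
| 120 | 180 | 180 − 122 = 58 | 180 − 134 = 46 |

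These are nominal dates. With ±7 days on sessions and ±7 (day 90) or ±14 (day 180) on visits, a single wait could move by up to 7 + 7 = 14 or 7 + 14 = 21 days. The last session nominally falls at baseline day 182 to 194, after the day-180 visit. SAP 5.2 expects this, since it counts participants whose final session follows that assessment. An earlier event first disclosed there has no later research visit to catch it.

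**Step 3: who might have no later visit.** Inputs: 90 participants randomised 1:1, so 45 per group; 75% retention at 6 months and a minimum of 33 per group with outcome data (17.1).

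- 45 × 0.25 = 11.25
- 45 − 33 = 12

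So at most about 11 to 12 FIT participants lack a day-180 visit. This is a ceiling: it includes any who died, withdrew or stopped FIT. A missed event needs someone who keeps attending FIT, misses the research visit (or does not mention the event there) and tells only the ALN. The documents do not say how many that would be.

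**The case against.** The strongest case against is that 16.3.1 is a supplementary route, and much of it stands.

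- **Admissions do not simply go unreported.** A reader might infer that they do. But research contacts cover both arms on one schedule with no causality filter, and resource-use recall runs from discharge to day 90 and from day 90 to day 180 (10.3, 10.4). Late, or missed if later contacts fail, is as far as the text goes.
- **There are other back-ups.** Protocol 4.4 and SAP 3.4.3 allow re-hospitalisation to be taken from hospital records at participating sites, and 10.6 permits contact with the GP. These help only in part: the records serve an outcome and are not named as an SAE source. Nor is the ALN the sole safety mechanism: 16.9 adds monthly management group discussion and quarterly steering committee review.
- **ALNs are not barred from reporting more.** Section 16.3.1 sets a minimum and is silent on the rest. The clinical trials unit's instructions to sites, promised in 16.3 and not available here, might ask for all SAEs. That lowers confidence about practice but leaves the protocol's own text inconsistent.
- **Unrelated SAEs reach the sponsor and steering committee quarterly anyway** (16.6), and the waits above are under one quarter. This does not answer the 24-hour rule or the immediate notice to the CI, which apply to all SAEs.
- **The narrow rule protects comparability.** FIT sessions exist in one arm only, so an all-events duty on ALNs adds a detection route in that arm and could inflate its SAE count. This is a real cost. It is better met by recording the route of detection than by leaving known SAEs to the ALN's view of cause.

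**Conclusion.** The point holds as an inconsistency that should be corrected. The only written ALN duty in 16.3.1 carries a causality condition that 16.1 does not recognise, and it puts the therapist's judgement ahead of the assessors named in 16.4 and 16.5. The consequence is limited: SAEs first disclosed in a FIT session may reach the PI about 20 to 88 days later than they could, or be missed if the participant does not attend, or does not mention the event at, a later research contact.

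The range rests on discharge 2 to 14 days after baseline, nominal visit dates and no other disclosure in between. The 11 to 12 of 45 is an upper limit on participants without a day-180 visit. It should not be read as a forecast of lost events, because the documents give no rate of admission, of disclosure to ALNs, or of FIT attendance among people who miss research visits.

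**What to change.** - **Protocol 16.3.1.** Reconcile it with 16.1, 16.4 and 16.5: the ALN tells the site PI of any event meeting 16.1, whatever its believed cause; the PI assesses causality and applies the 24-hour rule. State in 16.5 that the clock runs from the ALN's awareness too.
- **eCRF.** Add one field for how each SAE was first detected: research visit, records or FIT session.
- **SAP 5.4.** Present by-group SAE counts twice: for all events, and for events found at research visits or in records. The second comparison uses routes open to both arms.

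The cost is a short amendment, one data field and one extra row in the SAE table. The downside is more SAEs entered for the FIT arm through its extra contacts, which the second count addresses.

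The SAP's revision record shows that version 1.1 followed database lock, so the data-collection changes may come too late for this pilot. In that case, state the limitation when SAEs are reported and correct the rule for the definitive trial.
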